Hyaluronate [Viscoseal] Injection after Knee surgery; an Evaluation

A multi-centre, randomised, single-blinded trial assessing patient and clinical outcomes of Viscoseal injection after meniscal repair surgery

Version 1.3, dd 21 May 2021

Chief Investigator's Statement of Ownership and Content.

I, [name], confirm that this protocol is my work and is owned by me. The protocol conforms with standards outlined in the Declaration of Helsinki 1964.

Name (PRINT):______
Signature:_____
Date: _____

IRAS ref 272362 Page **1** of **30**

RESEARCH PROTOCOL SUMMARY

TITLE:	A multi-centre, randomised, single-blinded trial assessing
	patient and clinical outcomes of Viscoseal injection after
	meniscal repair surgery
Short title:	HIKE trial (Hyaluronate [Viscoseal] Injection after Knee surgery; an
IDAC mumahan	Evaluation)
IRAS number	272362
Device description	'Viscoseal' , a 0.5% sodium Hyaluronate solution in a
	10 ml bottle. To be administered intra-articularly.
	Active ingredient - Sodium hyaluronate
	Excipients - Sodium chloride, Sodium
	monohydrogenphosphate, sodium dihydrogenphosphate,
	water for injection.
	Duration of treatment: Single instillation at the end of
	arthroscopy and after completion of normal irrigation process.
	Current usage: Licensed and widely used throughout the UK
	and Europe for arthroscopic procedures. Viscoseal is devoid of
C. I.	animal proteins and hence has negligible allergenic potential.
Study type	Medical device randomised controlled trial, involving CE-
	marked devices used for intended purpose.
Study design	Single-centre, two-arm (1:1 allocation), single-blinded,
	prospective randomized trial.
Patient population	Total of 52 patients, aged 18-59 and BMI < 35, with MRI-
	confirmed meniscal injury who are eligible for meniscal repair
	surgery due to associated pain and impaired knee joint
	functionality. Previous knee surgery on index leg,
	accompanying ligament injury, and advanced knee
	osteoarthritis are the main exclusion criteria.
	For MRI imaging pilot sub-study, a total of 24 patients (out of
	the above 52 patients) will be enrolled.
Primary objective	To assess the efficacy of Viscoseal for reduction of post-
,,	operative pain after arthroscopic meniscal repair surgery
	when compared with standard care.
Secondary objectives	To assess the efficacy of Viscoseal for reduction of post-
	operative swelling after arthroscopic meniscal repair surgery
	when compared with standard care.
	To assess the efficacy of Viscoseal for improvement of post-
	operative patient-reported outcome measures, including pain
	upon walking and knee functionality, after arthroscopic
	meniscal repair surgery when compared with standard care.

IRAS ref 272362 Page **2** of **30**

	To evaluate, as part of a pilot sub-study, if there are any differences in terms of meniscus and knee joint recovery by means of radiological examination using MRI.
Sponsor	North Cumbria Integrated Care NHS Foundation Trust
Manufacturer & research grant provider	Manufacturer and distributor: TRB CHEMEDICA (UK) LTD [name]
Chief Investigator	[name], consultant Orthopaedic Surgeon. North Cumbria Integrated Care NHS Foundation Trust. Phone numbers: [name], [contact]
Co-investigators	[name], Orthopaedic Specialist Practitioner, North Cumbria Integrated Care NHS Foundation Trust, [contact]
	[name] PhD, Science & Innovation Manager, North Cumbria Integrated Care NHS Foundation Trust, [contact]
	[name], Consultant Radiologist, North Cumbria Integrated Care NHS Foundation Trust, [contact]
Organisations where research will take place	North Cumbria Integrated Care NHS Foundation Trust Orthopaedics Department, Cumberland Infirmary, [name] / Westcumberland hospital, [name] [CI [name]]
	The Royal Orthopaedic Hospital NHS Foundation Trust, [name] [PI [name]]
	Warrington & Halton Hospitals NHS Foundation Trust, [name] [PI [name]]
Planned timeline	Recruitment start date (first patient, first visit) 1 Jan 2020 Recruitment end date (last patient, first visit): 1 July 2022 Recruitment end date (last patient, last visit): 1 Jan 2023
Protocol version, date	Version 1.3, dd 21 May 2021

IRAS ref 272362 Page **3** of **30**

IRAS ref 272362 Page **4** of **30**

1. LAY SUMMARY

Arthroscopic, or keyhole, surgery of the meniscus in the knee joint has benefits over open surgery. Nonetheless, there is scope to further improve outcomes for patients by reducing pain and discomfort and promoting enhanced recovery of knee joint functionality. The medical device Viscoseal contains hyaluronan and is designed to replenish levels of this compound in the knee joint following arthroscopic repair of the meniscus. Naturally, synovial fluid in the knee joint contains hyaluronan, but a lot of it is washed away when surgeons flush the knee joint during surgery to remove loose pieces of meniscus, cartilage, or bone. Previous studies, both in laboratory studies and patient trials, have demonstrated that Viscoseal can promote re-establishment of biological structure in the knee joint to allow it to return to a normal physiological state and protect cartilage. This present prospective, randomised, controlled trial aims to build on this evidence by comparing standard care versus the injection of Viscoseal (26 vs 26 patients) at the end of arthroscopic meniscus surgery. The degree of pain, leg swelling and knee functionality experienced by patients after surgery will be measured using validated patient surveys focused on the meniscus. The main objective is to determine if Viscoseal can achieve a minimal clinically important difference in pain relief after meniscal repair surgery when compared to standard care.

IRAS ref 272362 Page **7** of **30**

2. INTRODUCTION

Arthroscopic surgery confers significant benefits on the recipient over and above those associated with open surgical procedures. The technique offers less insult to the structures being operated on and the surrounding architecture, decreases the risk of complication and infection, and reduces pain, hospitalisation time, and recovery time. The knee is the largest synovial joint, with a shared capsule enveloping the medial tibio-femoral (MTF), lateral tibio-femoral (LTF), and patella-femoral (PTF) compartments. The knee affords a number of congruent articulations where degenerative or traumatically induced changes may manifest. Arthroscopic knee surgery is a widely practised operation used to remove osteophytes, calcium pyrophosphate dehydrate (CPPD) deposition, and loose bodies. Debridement of irregular condylar surfaces may also be effected during this type of procedure. The knee houses meniscal structures composed of fibrochondrocytes enveloped in a matrix containing highly oriented Type 1 collagen fibres. Damage to these structures can be treated, the objective of meniscal repair being to obtain not only a stable but also a completely healed tear. However, where repair is not possible or practicable, meniscectomy can also be carried out arthroscopically.

As with any surgical intervention there can be side effects associated with arthroscopy, primarily these are pain, swelling and loss of joint mobility; surgical trauma can contribute to this [1,2,3] Usually 1-2 litres of saline is used as an irrigating medium during a simple arthroscopic procedure. Because the irrigation solution washes out the synovial fluid (SF) that resides in all synovial joints, the protective and lubricating functions of the SF are temporarily absent, and several days may elapse before the joint begins to replace the fluid that has been lost. Additional problems arise due to the fact that irrigation solutions may have a negative effect on the metabolism of articular cartilage (1-3), and reduced mobility due to arthroscopy may lead to decreased production of endogenous hyaluronan. Further deleterious processes, brought about by the commonly practised instillation of intra articular local anaesthetic at the end of the procedure, reportedly deplete cartilage integrity, and compromise chondrocyte synthesis and disrupt collagen structures in hyaline matrices. (4-7).

Hyaluronan is a normal vital constituent of both articular cartilage and synovial fluid. It is an unbranched high molecular weight polysaccharide belonging to the family of glycosaminoglycans. A major role of Hyaluronic Acid (HA) is to maintain the structural and functional characteristics of the extra-cellular matrix of articular cartilage, and - in its unaggregated form – polymerise the synovial fluid. It is ubiquitous throughout the human system in the interstitial space [8]. Viscoseal (TRB Chemedica) is a 0.5% concentration, isotonic solution of hyaluronan of fermentative origin. It is designed as a synovial fluid substitute for use following arthroscopic surgery or joint lavage. Instilled into the joint immediately after surgery, Viscoseal purportedly acts as a temporary substitute for the synovial fluid (SF) that has been lost during arthroscopy, performing the lubricating, shock absorbing and filtering functions of this fluid. In addition, it displaces any irrigating solution left in the joint space, preventing impairment of cartilage metabolism.

IRAS ref 272362 Page **8** of **30**

The introduction of Viscous Sodium Hyaluronate into the joint space re-establishes the protective coating of Hyaluronan over the surface of the articular cartilage and synovial membrane. By replacing the superficial layer of viscous Hyaluronan on the intima of the synovium, potential innervation of pain receptors is reduced. This reduction in pain helps to enhance joint mobility, which in turn promotes the production of endogenous Hyaluronan.

Sodium Hyaluronate has been used extensively in the treatment of osteoarthritic joints. Intraarticular injection of exogenous hyaluronan has been demonstrated to be useful in relieving pain and improving function in degenerative knee joints in randomised controlled trials. The benefits persist for approximately 6 months, with no serious adverse effects. [8,11,12,13,14]. In addition, reports have shown that exogenous hyaluronan promotes tissue healing [15,16] and protects articular cartilage and synovial membrane from damage following the experimental initiation of joint disease [17]. Exogenous hyaluronan has been used following arthroscopy in other joints, demonstrating significant benefits with no reported complications [18,19]. Randomised trials involving the administration of Viscoseal in meniscal repair and meniscectomy surgery also demonstrated positive effects. Early and medium term pain experienced by patients was lower in those treated with Viscoseal. Furthermore, post-operative leg swelling was reduced in the two weeks following the procedure when compared to patients who had not received Viscoseal [20-21]. One study failed to see an effect of HA on recovery after partial meniscectomy [22]; however, patients only received 24 mg of HA (Hymovis 24 mg/3 mL; Fidia Farmaceutici SpA) whereas the Viscoseal dose is 50 mg (10ml at 0.5%). Another limitation of that particular study is that some of the outcome measures were not optimal for meniscal surgery, such as the Knee injury and Osteoarthritis Outcome Score (KOOS) which is primarily used for knee replacement surgery. The same measure was used by Thein et al [20], and they could not detect a difference between control and Viscoseal cohorts either. HA, through application of Hymovis, may even contribute to reduced pain and a degree of meniscal tear healing when it is administered as a conservative treatment without surgical intervention [23]

This present study further investigates the effects of instilling 10ml of a 0.5% Sodium Hyaluronate of fermentative origin (Viscoseal) into the capsule at the end of arthroscopic meniscal surgery. By displacing residual saline and debris from the surrounding soft tissue and exposed cancellous bone, and establishing a viscous, protective barrier over localised nociceptors, it is hypothesised that a more favourable patient outcomes – as evinced by meniscus-specific validated scoring instruments - will be achieved.

3. INVESTIGATIONAL DEVICE & INTERVENTION

3.1 Investigational device

'Viscoseal' is a 0.5% sodium hyaluronate solution in a 10 ml bottle. It is administered intra-articularly as a single instillation at the end of arthroscopy and after completion of normal irrigation (lavage) process. The active ingredient is sodium hyaluronate, and the excipients are sodium chloride,

IRAS ref 272362 Page **9** of **30**

sodium monohydrogenphosphate, sodium dihydrogenphosphate, and water. The product is licensed and widely used throughout the UK and Europe for arthroscopic procedures. Viscoseal is devoid of animal proteins and hence has negligible allergenic potential.

3.2 Intervention

3.2.1 Standard care (control) arm

All patients receive general anesthesia and a pneumatic tourniquet is used. Patients are already randomised prior to surgery to avoid delays with surgery and allow a vial of Viscoseal to be ready for the relevant patients. Joint irrigation is performed with the assistance of a manual arthroscopic pump using 0.9% NaCl solution at room temperature. Then, the remaining fluids are drained from the knee. At the end of the surgery, local anaesthetics is applied to the soft tissue of the arthroscopic portals [either 20 ml 0.5% Levobupivacaine (Chirocaine®), or 20 ml 0.75% Ropivocaine (Naropin®), or equivalent product], and the knee is dressed, while the tourniquet is still inflated. All surgeries are intended to be performed in a day-surgery facility with the patient being discharged the same day. Postoperatively, partial weight bearing with crutches is allowed. Crutches are recommended for the first 48 hours, primarily for patient safety by minimising the risk of a fall.

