5.3 Consent and recruitment

Those eligible will be approached and provided with an information pack and consent form, which will be signed to indicate that informed consent has been given. Patients will be given ample time to consider taking part, more than 24 hours if they wish. The study will be first mentioned at an orthopaedics out-patient clinic visit. The direct healthcare professional will first approach a patient about the study, and after verbal consent by the patient the healthcare professional themselves or a member of the research team can go through the informed consent process.

Patients are also allowed to consent to taking part when first approached as long as the study has been discussed with the patient and they have been given time to read the patient information leaflet and opportunity to ask any questions that they may have. Participants will receive no incentives and consent will be regarded as a process and not a one-off event. Participants are free to withdraw from the study at any time without the need to give any reasons for withdrawal. Their standard of care will not be affected by either declining to participate in the study or withdrawing during participation. Data collected up to the date of withdrawal will be retained for analysis.

Participants will be randomised to either the treatment as usual (TaU) or the intervention group (Viscoseal) any time up until the day of surgery. Study subjects who subsequently require additional significant surgical intervention, primarily ligament reconstruction, will be withdrawn from the study.

The MRI sub-study will be offered to all patients consecutively, and this will be done until the 24 required patients for said sub-study have been recruited.

5.4 **Follow-up**

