5.5.3 MRI sub-study outcomes measures

Assessment of length and depth of meniscal tears will be performed by a radiologist using MRI at baseline and 26 weeks after surgery. The radiologist will be blinded to the patients' study allocation. The following standard grading system will be used to describe abnormal intrameniscal signals: Grade 1 – the signal is oval or globular in appearance and does not communicate with any meniscal surface; Grade 2 – the signal is a more linear but, similarly, does not communicate with the articular surfaces; Grade 3 - the signal, located within the meniscus, is linear and should communicate with either the superior or the inferior articular surfaces. Grade 1 and 2 signals are consistent with intrasubstance myxoid degeneration, whereas a Grade 3 signal is consistent with a tear. Tear patterns will be classified as longitudinal (located anywhere along the meniscus), horizontal (begins at the inner margin of the meniscus and extends towards the capsule), radial (begins at the inner margin and extends towards the capsule) or flap (either a vertical flap tear or a horizontal flap tear). By comparing the follow-up MR images with the baseline images, the presence or absence of a reduction in length and depth of the lesion can be identified. The occurrence of a new lesion with respect to baseline will be considered as a deterioration/recurrence and recorded as an adverse event. Reductions in the length and depth of the meniscal tear subsequent to baseline, assessed radiologically, were measured in relation to the index tear evaluated at baseline.

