6.1.1 Randomisation

Following written consent, participants are allocated at random to the control or Viscoseal intervention group, using a randomised sequence from the freeware randomisation programme, see https://www.randomizer.org/.

To take into account that not all patients will consent to taking part in the MRI sub-study, two randomisation sequences will be produced. One for patients who consent to both trial and MRI sub-study and one for patient who only consent to the main trial. This means:

- 24 patients for main trial + MRI sub-study (12 control and 12 Viscoseal)
- 28 patients for main trial only (14 control and 14 Viscoseal).

In this manner both control and Viscoseal arms are equally represented in the MRI sub-study and the remaining patients for the main trial are also equally distributed amongst the two study arms.

If one of the two randomisation blocks is full, then only the remaining block will be recruited to. However, North Cumbria Integrated Care is the only NHS Trust to conduct the MRI-substudy.

Sequential envelopes with each next randomisation allocation (for each randomisation block) will be used to achieve concealment and these will be kept in the research department. The researcher or regular healthcare professional for the participant in question can e-mail ([contact]) or phone the R&D Dept ([name]) to determine which treatment the next participant has been allocated to.

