6.2.1 Inclusion criteria

- Patients has mechanical symptoms and pain and MRI evidence of meniscal tear, amenable to surgical repair
- Meniscal surgical repair of the knee for meniscal tear grade III
- Proficient in English (reading and writing, due to surveys being sent electronically)
- Adult patients aged > 18 years and < 60 years
- Mental capacity to give written informed consent and follow trial measurements

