8. STATISTICAL CONSIDERATION AND DATA ANALYSIS PLAN

8.1 Analysis of baseline characteristics

To determine the demographics and characteristics of the patients in the two arms the following data will be collated:

- Age (yrs)
- Gender

IRAS ref 272362 Page **18** of **30**

• Height (kg), weight (cm), BMI

Distribution of data will be summarised but no inferential statistics will be applied in line with guidance [26].

Data concerning the actual meniscal repair procedure will also be collected, including:

- Exact meniscal surgery carried out (repair, partial meniscectomy, complete meniscectomy)
- Length of operation (min) and blood loss (ml) during operation
- Details on lavage procedure, if deviation from standard procedure.
- Type of anaesthetic and analgesics prescribed post-surgery
- Hospital length of stay (days)
- Moment physiotherapy and early recovery initiated, if applicable
- Any analgesics and/or anti-inflammatories administered and/or prescribed.

Any differences in distribution will be established with Chi-squared test or Mann-Whitney U-test/t-test (depending on distribution of data) as indicated.

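### Allocation is made and can be known before surgery, but repair versus meniscectomy, an eligibility criterion, is finally decided in theatre, and nothing keeps a converted patient in the analysis

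*Protocol*

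**What the plan says.** **Timing of allocation.** Section 3.2.1: "Patients are already randomised prior to surgery to avoid delays with surgery and allow a vial of Viscoseal to be ready for the relevant patients". Section 5.3 allows randomisation "any time up until the day of surgery".

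**Who can know the arm.** Under section 6.1.1 the envelopes stay in the research department, but the researcher or the participant's usual healthcare professional may e-mail or phone "to determine which treatment the next participant has been allocated to". The protocol summary describes the design as "Single-centre, two-arm (1:1 allocation), single-blinded". The only assessor expressly masked is the MRI reader, in section 5.5.3: "The radiologist will be blinded to the patients' study allocation". Nothing is said about masking the surgeon or theatre staff.

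**Eligibility.** Section 6.2.1 asks before surgery for "Patients has mechanical symptoms and pain and MRI evidence of meniscal tear, amenable to surgical repair". It also lists the surgical repair itself as an inclusion criterion, and section 6.2.2 lists meniscectomy, unqualified, as an exclusion.

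**What may happen in theatre.** The Introduction notes that "where repair is not possible or practicable, meniscectomy can also be carried out arthroscopically". Section 8.1 collects for trial patients: "Exact meniscal surgery carried out (repair, partial meniscectomy, complete meniscectomy".

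**What happens next.** Sections 5.3 and 6.3 withdraw patients who later need further significant surgery, chiefly ligament reconstruction. Neither mentions conversion to meniscectomy. For withdrawn patients, section 5.3 keeps the data collected so far and section 6.3 removes them.

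**The concern.** Randomisation protects the comparison only if what happens after it cannot select patients differently by arm. Here one eligibility criterion is the operation performed, and that is known for certain only after allocation. If a converted patient is then treated as ineligible, the exclusion depends on a surgical judgement that may have been made with the arm known.

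Two things are at stake. The evaluable number falls, in a trial whose two sequences add up to exactly 52 and for which no replacement is described. And if exclusions differ between arms in a way related to prognosis, the day-7 pain comparison is biased. That outcome is self-reported.

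**Working it through.** **1. Can the exclusion act after randomisation?** In order: MRI suggests a repairable tear (6.2.1); consent; allocation, at the latest on the day of surgery (5.3); vial readied for Viscoseal patients (3.2.1); arthroscopy, where the procedure is settled and recorded as repair or meniscectomy (8.1); drainage and, in one arm, a single instillation (3.1, 3.2.2). The procedure-based criterion is resolved after allocation. No sentence says whether a patient who fails it then stays in or comes out.

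**2. Does delivery of the device need early allocation?** No. It is instilled once, after drainage. Section 3.2.1 gives a logistic reason: avoiding delay.

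**3. The plan's own sample size.** Inputs from section 6.1 and Table 3: difference 15 mm, SD 20 mm, effect size 15/20 = 0.75, alpha 0.05, stated as two-sided Mann-Whitney. Power is taken from the noncentral t distribution with each arm's n multiplied by the asymptotic relative efficiency 3/π = 0.955 (normal data).
- At 24 per arm (the stated 48): 80.4% one-sided, 70.0% two-sided. The stated 48 is reproduced one-sided only. That is a separate matter, but it means the two-sided figures below start low.

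**4. Loss of power.** The conversion rate is an assumption: 5–15% of 26 is 1.3 to 3.9, so about 1 to 4 per arm. Noncentrality = 0.75 × √(0.955 n / 2).

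| Evaluable per arm | Noncentrality | Two-sided power |
|---|---|---|
| 26 | 2.643 | 73.5% |
| 22 (4 excluded per arm) | 2.431 | 66.0% |

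The cost at the upper end is 7.5 percentage points. After the planned 10% attrition (26 × 0.9 = 23.4 per arm) power is 68.8%. Excluding a further 10% of each arm leaves 21.1 per arm and 64.0%.

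**5. Possible bias.** Suppose k of 26 patients with the worst prognosis are removed from one arm and none from the other. With SD 20 and correlation r between the prognosis seen in theatre and day-7 pain,

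shift = r × 20 × (sum of the k largest expected normal order statistics of 26) / (26 − k).

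The three largest are 1.98, 1.54 and 1.28, so the sums are 3.52 (k = 2) and 4.81 (k = 3).

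| k | r = 0.3 | r = 0.5 |
|---|---|---|
| 2 | 0.9 mm | 1.5 mm |
| 3 | 1.3 mm | 2.1 mm |

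As a share of 15 mm: 0.88/15 = 6% to 2.09/15 = 14%. At r = 0 the shift is nil.

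**6. Cross-check by simulation.** With no true effect, 24 per arm before exclusion and 20,000 replicates, removing the worst-prognosis 10% from one arm only gives a shift of 1.2 mm (r = 0.3) to 2.0 mm (r = 0.5) and a two-sided type I error of 5.3% to 5.9%. Removing 10% from both arms by the same rule gives no material shift and a type I error of 4.9%.

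**The case against.** The strongest reply is that the protocol never says converted patients are removed. Its withdrawal rule names ligament reconstruction, not meniscectomy. The screening form is completed before surgery, so the exclusion can be read as meniscectomy planned at entry. Recording the procedure in section 8.1, with a test of differences between arms, suits a trial that keeps and describes such patients. Analysis populations are often left to the SAP, which is not at hand. All of this stands as a possible reading. But the exclusion is unqualified and the repair itself is an inclusion criterion, so the opposite reading is equally open. The timing of allocation is fixed in the protocol, not left to the SAP.

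Three stronger inferences are tempting, and the documents do not support them:
- *That repairability is judged only at arthroscopy.* Section 6.2.1 requires a first judgement on MRI.
- *That the surgeon knows the arm.* This is not stated. The vial and the access to allocation make it possible, and nothing prevents it.
- *That the bias could reach 2.9–4.2 mm, up to 28% of the target.* That needs r = 1, that is, patients ranked on the day-7 score itself, which nobody has in theatre.

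It is also fair that, if converted patients counted as withdrawals, the 10% attrition allowance would absorb some of them. And late opening of the allocation has a real cost: the envelopes sit in one research department, the summary lists other Trusts, and section 3.2.1 gives avoidance of delay as its reason for early allocation.

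**Conclusion.** The point holds as a weakness of design, not as a demonstrated bias. A randomised patient can fail a procedure-based criterion in theatre, when staff may know the arm, and no text says the patient is then kept.

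Its size rests on assumptions, because the protocol gives neither a conversion rate nor a link between surgical findings and pain. At an assumed 5–15% conversion, up to about 7.5 points of power are lost (73.5% to 66.0%). Bias arises only if removal differs between arms in a way related to prognosis. For 2–3 patients and a correlation of 0.3–0.5 it is about 1–2 mm, or 6–14% of the 15 mm target. This is modest but avoidable, and a change should be made.

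**What to change.** **Preferred.** Leave consent and assignment to the two sequences as they are. Have the sealed next allocation and an unopened vial available in theatre for every consented case, and reveal the allocation only once the surgeon has confirmed that the repair has been done. This removes both the selection and the conversion losses, and having the vial to hand answers much of the concern about delay. The cost is a short amendment, one extra step at closure, and either transfer of the sealed allocation to theatre or a call to the research department while the patient is still in theatre. The other Trusts need the same arrangement.

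**If the present timing is kept to avoid delay.** Add to section 6.2.2 that the meniscectomy exclusion applies only to meniscectomy planned at consent, with the repair criterion in section 6.2.1 worded to match. Add to section 8.2 that every randomised patient stays in the primary analysis as randomised, whatever meniscal procedure is performed. This costs a few sentences.

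Either way, reconcile sections 5.3 and 6.3 on the data of withdrawn patients.
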